### **Protocol deviators**

All completers in the intervention group who are not considered as having fully or partially followed the protocol (i.e per protocol or partial per protocol).

Data related to measures of adherence will be presented for all completers, item non-responders and for per protocol completers and partial per protocol completers. The distribution of the outcome will be visually inspected using QQ-plots and histograms and if Gaussian distributed it will be presented as means and standard deviations; if not it will be presented as medians (25th and 75th percentiles).

## **Protocol deviations and changes of the intervention delivery and health examinations during the COVID-19 pandemic**

During the COVID-19 pandemic and lock-down period in Denmark, the health examinations and the delivery of the intervention had to be adapted to national and local restrictions and reconsidered to minimise risk and concerns of the participants and the intervention deliverers.

During the first lock-down from March 2020 to June 2020 (4 months), the baseline and follow-up health examinations were conducted at the three sites. However, it was decided to implement a wider time span for attending the baseline examination (up to 21 weeks after delivery) and no time limit for participation in the follow-up-examination, in order to secure a medical and ethical treatment of participants by offering a health examination as planned. During the same period, the delivery of home visits by health visitors, as a part of the intervention activity, were postponed or converted to online visits. Therefore, a few participants did not receive three visits as expected; however, in line with the re-opening of society (late spring 2020), physical home visits were reimplemented (with protective adaptations).

During the second lock-down from December 2020 to March 2021 (4 months), the health examinations were conducted similar to the first lock-down. The delivery of the intervention was adapted due to local restrictions for health visitors in the municipalities. Overall, the guidance was to prioritise home-visits. Online visits were offered if the participants expressed any concerns or if the health visitor assessed it as preferable to minimise the risk of COVID-19.

From November 2021 to May 2022 (5 months), the COVID-19 pandemic resulted in temporary local restrictions for health visitors in the municipalities, however, with minor consequences for the trial and intervention delivery.

From June 2021 to August 2021 (2 months), a national strike among selected groups of nurses affected one of the intervention municipalities (Aarhus), which resulted in the postponement of a few home visits or that two visits were converted to one if time to health examination date was limited.

All adaptations were recorded in a log.

Due to challenges in the recruitment process, primarily due to a temporary stop for recruitment of women during the first lock-down from March to June 2020 and an unexpected high number of women giving birth at the trial hospitals with a residence in municipalities not included in the trial, we decided to expand the geographic recruitment area. This expansion was initiated on August 1, 2020, and included possibilities for recruitment from all municipalities within Funen and municipalities within 45 km from Aarhus municipality, in addition to recruitment of participants residing in Odense and Aarhus municipality. The aim was to speed up the recruitment process of women to the project. Consequently, a few of the second or third home visits were adapted to either online or being accomplished at the “Sundhedshuset” – a formal workplace for health visitors in Odense Municipality.

## Section 4: Trial population

### Eligibility, inclusion, and exclusion

Inclusion and exclusion criteria are defined in detail in the Face-it trial protocol.

Eligibility and inclusion criteria:

- Women with a GDM diagnosis when attending or giving birth at one of the three recruiting hospitals. According to Danish guidelines, GDM is diagnosed when, following a 75 g oral glucose tolerance test (OGTT), the 2 h value is  $\geq 9.0$  mmol/l (venous plasma or capillary blood)
- Live in either Aarhus, Copenhagen, or Odense municipalities
- Able to understand and provide written informed consent in Danish

Exclusion criteria:

- Concomitant participation in other postpartum intervention
- Overt diabetes at baseline

The flow chart of the trial will comply with the CONSORT guidelines and will include the number of individuals who a) were invited during pregnancy b) consented to participate in the trial, c) attended baseline examination, d) were randomised at baseline, e) were lost to follow-up and f) were analysed for follow-up.

### Withdrawal/loss to follow-up

If a randomised participant withdraws from the intervention, she will be offered to participate in the final follow-up examination. Participants without body weight measurement at V2 will be regarded as lost-to-follow-up in regard to the primary outcome on BMI during the intervention period. Participants without completed SF-12 questionnaire at V2 will be regarded as lost-to-follow-up in regard to the primary outcome on Quality of Life. In addition, participants who are pregnant at follow-up (V2) will also be considered lost to follow-up in the outcome analyses. The number of participants lost-to-follow-up for each group will be reported in a CONSORT diagram. If possible, the reasons for participants not completing the trial will be given. Summary of baseline levels for variables reported in the baseline table will be provided for completers, item non-responders and non-completers.

### Baseline characteristics

The distribution of all continuous outcomes and included baseline characteristics will be visually inspected using QQ-plots and histograms; those with a Gaussian distribution will be presented as means and standard deviations and those with a non-Gaussian distribution will be presented as medians plus 25th and 75th percentiles (IQR), number of observations will be presented for each outcome presented. Categorical data will be summarised by numbers and percentages. Tests of statistical significance will not be undertaken for baseline characteristics; rather the clinical importance of any imbalance will be noted.

The following outcomes will be included in the baseline participant characteristics table for all participants combined and stratified by randomisation group:

- Time from delivery to baseline (weeks)
- Age (years)
- Parity (n and % primiparous)
- Has a partner (n and %)
- Partner participating in the Face-it study (n and %)
- Study site
  - Copenhagen (n and %)
  - Aarhus (n and %)
  - Odense (n and %)
- Country/Region of birth
  - Denmark (n and %)
  - Europe
  - Asia
  - Other
- Education
  - Low education (n and %)
- Employed (n and %)
- On maternity leave at baseline (n and %)
- Current tobacco use (n and %)
- First degree family history of diabetes (n and %)
- Insulin use during last pregnancy (n and %)
- Use of glucose lowering medication at baseline (n and %)
- Pre-pregnancy BMI (kg/m^2)
- BMI at baseline (kg/m^2)
- Weight at baseline (kg)
- Waist circumference (cm)
- Hip circumference (cm)
- Body fat%
- Fasting glucose (mmol/L)
- 2h glucose (mmol/L)
- HbA1c (mmol/mol)
- Impaired Fasting Glucose (n and %)
- Impaired Glucose Tolerance (n and %)
- Fasting insulin (pmol/L)
- 2h insulin (pmol/L)
- HOMA-IR
- HOMA- $\beta$
- Systolic blood pressure (mmHg)
- Diastolic blood pressure (mmHg)
- Total cholesterol (mmol/L)
- HDL cholesterol (mmol/L)
- LDL cholesterol (mmol/L)

- Triglycerides (mmol/L)
- SF12
  - Self-perceived health
    - Excellent/Very good (n and %)
  - Mental component score
  - Physical component score
- Perceived stress scale score
- WHO-5 percentage score
- General Anxiety Disorder (GAD-7) score
- Dietary Quality Scale (DQS)-2017 score
- IPAQ-SF
  - Walk (min/day)
  - Moderate to vigorous activity (min/day)
- Currently breastfeeding (n and %)
- Social support for Diet and Exercise
  - Encouragement Family scale
  - Participation Family scale
- TSRQ Exercise self-regulation and motivation
  - Autonomous scale score
- General self-efficacy
- RPS-DD Risk perception
  - Perceived risk of getting diabetes
    - Moderate/high (n and %)
  - Made behaviour changes to change risk of diabetes,
    - Yes (n and %)
- HLQ Health literacy
  - Domain 3 Actively engage my health
  - Domain 6 Ability to actively engage with healthcare providers

## Section 5: Analyses

### Outcome definitions

#### *Primary outcomes*

The primary outcomes, BMI and Quality of Life, are assessed at V1 and V2. BMI is calculated from measured height and weight (measured to the nearest 0.1 kg). Quality of life is measured with the SF-12 mental component score. The treatment effect will be given as the baseline corrected differences in kg/m^2 and SF-12 mental component score, respectively, between the groups at V2

#### *Secondary outcomes*

The treatment effect will be given as the baseline corrected difference between the groups at V2. The secondary outcomes are grouped into two hierarchies.

#### Secondary outcomes in hierarchy 1 (BMI):

- Fasting glucose (mmol/L)
- HDL cholesterol (mmol/L)
- Triglycerides (mmol/L)
- Dietary Quality Scale (DQS)-2017 score
- IPAQ-SF
  - Moderate to vigorous activity (min/day)

#### Secondary outcomes in hierarchy 2 (Quality of Life):

- SF12
  - Self-perceived health, Excellent/Very good (n and %)
- Perceived stress scale score
- WHO-5 percentage score
- General Anxiety Disorder (GAD-7) score

### *Tertiary outcomes*

The treatment effect will be given as the baseline corrected difference between the groups at V2.

- Waist circumference (cm)
- Hip circumference (cm)
- Body fat%
- Weight change%
  
- 2h glucose (mmol/L)
- HbA1c (mmol/mol)
- Impaired Fasting Glucose (n and %)
- Impaired Glucose Tolerance (n and %)
- Fasting insulin (pmol/L)
- 2h insulin (pmol/L)
- HOMA-IR
- HOMA- $\beta$
- Systolic blood pressure (mmHg)
- Diastolic blood pressure (mmHg)
- Total cholesterol (mmol/L)
- LDL cholesterol (mmol/L)
  
- SF12
  - Physical component score
  
- IPAQ-SF
  - Walk (min/day)
- Breastfeeding duration (months)
  
- Social support for Diet and Exercise
  - Encouragement Family scale (Diet)
  - Participation Family scale (Exercise)
  -
- TSRQ Exercise self-regulation and motivation
  - Autonomous scale score
- General self-efficacy
- RPS-DD Risk perception
  - Perceived risk of getting diabetes, Moderate/high (n and %)
  - Made behaviour changes to change risk of diabetes, Yes (n and %)
  
- HLQ Health literacy
  - Domain 3 Actively engage my health
  - Domain 6 Ability to actively engage with healthcare providers

## Analysis methods

### *Analysis population*

The primary analysis is an intention-to-treat analysis (ITT) including all participants who will be analysed as randomised.

Prior to further analyses and unblinding, all variables will be inspected to detect outliers to identify potential data entry errors.

Descriptive statistics will be summarised by randomisation group (see Section 4, Baseline characteristics).

The intervention effect for the primary outcomes will be estimated as the difference in BMI by randomisation group adjusted for BMI at baseline as well as the difference in SF-12 mental component score by randomisation group adjusted for SF-12 mental component score at baseline analysed in mixed models. Intervention effect for secondary and tertiary outcomes will likewise be estimated as difference in the outcome by randomisation group adjusted for the outcome at baseline. Continuous outcomes will be analysed in mixed models with a random effect for hospital, categorical outcomes will be analysed in generalized linear mixed models (family binomial, link logit) with a random effect for hospital, and duration of breastfeeding will be analysed using Cox proportional hazards regression with robust variance estimates for clustering due to hospital.

Due to randomisation, baseline values will not be statistically tested between groups. Mean differences between the study groups will be analysed using analysis of covariance, adjusted for baseline levels. Study site will be included as a random effect in the mixed models. Sample size of the study was based to prove a difference in BMI of  $-1.0 \text{ kg/m}^2$  between the two randomisation groups ( $\text{SD } 2.5 \text{ kg/m}^2$ ,  $\alpha = 0.05$ , power 80%).

Between group differences will be null-hypothesis tested and presented with P-values. The following supplementary analyses are planned for the primary outcomes as well as the secondary and tertiary outcomes:

1. An analysis similar to the one described above but including the per-protocol analysis population only. We will carefully consider the findings from the ITT analysis when drawing conclusions based on the per-protocol analysis, including whether a potential statistically significant result of the per-protocol analysis may be due to selection or the intervention.
2. A sensitivity analysis, including the ITT analysis population, assessing the impact of missing data for the primary outcome. This analysis will only be performed in the case of a loss-to-follow-up rate  $> 10\%$ , i.e., more than 10% of all participants are missing at V2.
3. A sensitivity analysis excluding participants reporting use of glucose lowering medication at baseline.
4. A subgroup analysis stratified according to baseline BMI i)  $<25\text{kg/m}^2$  and ii)  $\geq 25\text{kg/m}^2$ .
5. A subgroup analysis stratified according to i) partner participation (defined as having a partner participating in the baseline visit) and ii) no partner participation (defined as not having a partner participating in the baseline visit).

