## Section 2: Study methods

### Trial design

Multicentre, randomised, two-arm parallel controlled trial consisting of a health examination 10–14 weeks after delivery (baseline V1) and 12 months after delivery (follow-up V2). Randomisation to intervention or usual care group is performed at baseline examination.

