### Sample size

Calculation of the projected sample size is based on individual changes in BMI among women with prior GDM after 12 months of follow-up. The mean changes are compared between the intervention and usual care group. We expect the mean change in the intervention group to differ by  $-1.0 \text{ kg/m}^2$  relative to the usual care group. The standard deviation of individual changes after 12 months is expected to be  $2.5 \text{ kg/m}^2$ . Based on a 2:1 randomisation procedure, a power of at least 80% and type 1 error of 5% (two-sided), a sample size of 225 will be required to detect such a difference in BMI. Assuming 30% of participants will be lost between baseline (after randomisation) and follow-up, we will need to include 322 women at baseline in the study. Because of the relatively long period (10–30 weeks) between recruitment and baseline and the exclusion of women with overt diabetes at baseline (before randomisation), we also assume that 30% of those agreeing to participate will withdraw before baseline data collection or be excluded (see section 4) before randomisation. We therefore need to recruit 460 women. For full details of the sample size calculation, please refer to Face-it trial protocol (2).

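### The primary BMI model is valid, but adding the already collected pre-pregnancy BMI as a second covariate would probably gain some precision at almost no cost

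*SAP*

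**What the plan says.** Under Analysis population in Section 5, the SAP estimates the primary BMI effect as the "difference in BMI by randomisation group adjusted for BMI at baseline". The same section adds: "Mean differences between the study groups will be analysed using analysis of covariance, adjusted for baseline levels". It also states: "Study site will be included as a random effect in the mixed models". The primary BMI model therefore has treatment group, V1 BMI and a random site effect, and nothing else.

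"Pre-pregnancy BMI" appears once, in the list under Baseline characteristics in Section 4. It enters no model, sensitivity analysis or subgroup analysis.

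Trial design in Section 2 puts V1 at 10–14 weeks after delivery and V2 at 12 months. The section on COVID-19 changes reports that the first lock-down brought "a wider time span for attending the baseline examination (up to 21 weeks after delivery) and no time limit for participation in the follow-up-examination", and that examinations in the second lock-down were run in a similar way.

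**The concern.** In many weight trials the baseline BMI is close to a steady state. Here it is measured a few months after delivery, so it may be the sum of a woman's usual BMI and whatever she still retains from pregnancy.

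As an illustration, take two women with a V1 BMI of 29 kg/m², one of whom was at 25 before pregnancy and the other at 29. If women tend to move back towards their earlier weight, the two have different expected V2 values. A model with V1 BMI alone treats them as the same, and the difference between them goes into the residual. The trial already holds the variable that would tell them apart.

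What is at stake is the width of the confidence interval for one of the two primary outcomes. Planned power has almost no reserve above 80%. Under the hierarchical procedure in Section 3, a failed BMI test also turns the later tests in that hierarchy into tertiary ones.

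**Working it through.** **Inputs from the SAP (Sample size, Section 2).** Difference 1.0 kg/m², SD of individual change 2.5 kg/m², 2:1 allocation, two-sided 5%, power at least 80%, 225 evaluable women (150 and 75). Loss of 30% is assumed after randomisation, and again before it.

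**Reproducing the plan's figures.**
- SE = 2.5 × √(1/150 + 1/75) = 0.354, so the noncentrality is 1.0/0.354 = 2.83.
- The noncentral t distribution gives 79.9% power at 222 women and 80.4% at 225. The stated 225 is right.
- 225/0.7 gives 322 after rounding up, and 322/0.7 = 460. Both stated totals reproduce.
- None of these figures relies on any gain from a covariate.

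**Why pre-pregnancy BMI carries the retained weight.** Write P for pre-pregnancy BMI. Then β₁·V1 + β₂·P = (β₁ + β₂)·V1 − β₂·(V1 − P). With V1 BMI in the model, adding P gives the same fit as adding the retained amount V1 − P.

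**Size of the gain.** Let r be the partial correlation of P with V2 BMI given V1 BMI. The residual SD becomes 2.5 × √(1 − r²). Two assumptions are needed, because the SAP supplies neither figure: a range for r, and 2.5 as the residual SD before P is added. Power uses the noncentral t, and the 95% CI half-width is t(0.975) × SE with t = 1.971. The last column is 1/(1 − r²) − 1.

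| r (assumed) | Residual SD | SE | SE falls by | 95% CI half-width | Power at 1.0 | Equivalent extra women |
|---|---|---|---|---|---|---|
| 0 | 2.500 | 0.354 | – | 0.70 | 80.4% | – |
| 0.1 | 2.487 | 0.352 | 0.5% | 0.69 | 80.8% | 1% |
| 0.2 | 2.449 | 0.346 | 2.0% | 0.68 | 82.0% | 4% |
| 0.3 | 2.385 | 0.337 | 4.6% | 0.66 | 83.9% | 10% |
| 0.4 | 2.291 | 0.324 | 8.3% | 0.64 | 86.7% | 19% |

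**What would produce such an r.** Suppose women lose on average a fraction b of the retained BMI between V1 and V2, and that retained BMI has SD s given V1 BMI. Then r = b × s/2.5. For b = 0.2 and s = 1, r = 0.08. For b = 0.3 and s = 2, r = 0.24. For b = 0.5 and s = 2, r = 0.40. All values of b and s are assumed. They show only that the table's range needs no extreme inputs, and that the gain could also be negligible.

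**Cost if r = 0.** One degree of freedom lowers power by about 0.002 percentage points, so it stays at 80.4%.

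**The case against.** The strongest reply is that nothing here is wrong. Analysis of covariance on the baseline value of the outcome is prespecified, unbiased under randomisation and keeps its type 1 error rate. The planned sample size already delivers the stated power. Any trial collects variables that could have been added to the model, and leaving one out is a choice. All of that stands.

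A reader might go further than the documents allow in four ways.

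- *That precision is being lost as a matter of fact.* The SAP does not say that BMI change depends on retained weight, and it gives no correlation. The mechanism is plausible given the timing of V1, but the gain is conditional on r.
- *That the trial is underpowered without the covariate.* At a true difference of 0.8 kg/m² power would be 61.5%, but that effect size appears nowhere in the SAP. At the planned 1.0 it is 80.4%.
- *That chance imbalance in retained weight is a defect.* The standard error already allows for it. The 2:1 ratio raises the variance of such an imbalance by only 12.5% over 1:1: (1/150 + 1/75)/(2/112.5) = 0.0200/0.0178 = 1.125. The SAP also tabulates pre-pregnancy BMI by arm and undertakes to note any clinically important imbalance.
- *That the same covariate should go into the models for waist, hip, body fat and weight change.* These are tertiary, descriptive outcomes, and no gain has been shown for them.

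Two practical cautions also stand. The SAP does not say how pre-pregnancy BMI is obtained or how complete it is, and error in it would shrink the gain. A rule for filling missing covariate values must also be squared with the Missing data section, which says without qualification that missing data will not be imputed. None of these points shows harm from adding the covariate.

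**Conclusion.** This holds as an inexpensive improvement to the primary BMI model, not as an error or contradiction in the plan. Pre-pregnancy BMI is fixed before randomisation, so adjusting for it introduces no bias, and it would probably narrow the confidence interval. Over the assumed range of r from 0.1 to 0.4, the standard error falls by 0.5% to 8.3% and power at the planned difference rises by 0.4 to 6.3 percentage points.

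The figures rest on the assumed r, on 150 and 75 women analysed, and on 2.5 as the residual SD. The SAP gives 2.5 as the SD of raw change. Adjustment for V1 BMI would leave a residual SD no larger than that, so the starting power may be slightly understated. The proportional fall in the standard error does not depend on the SD.

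**What to change.** Before the data are unblinded, make three changes to the SAP.

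1. Under Analysis population, add pre-pregnancy BMI as a fixed covariate beside V1 BMI in the primary BMI model. Leave the other outcomes as they are.
2. State that a woman without a pre-pregnancy value is given the overall mean together with a missing-value indicator, so that no randomised woman drops out of the analysis because of this covariate.
3. In the Missing data section, state that the rule against imputation concerns outcome data.

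The cost is a few sentences, one term in the model statement and one degree of freedom (a second if the indicator is needed), using data already collected. The benefit is smaller if pre-pregnancy BMI is measured with error. The timing matters: if made after unblinding, the same adjustment could look data-driven.

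### Yes/no outcomes cut from a measured or ordered variable are, read literally, adjusted only for the same yes/no split at baseline: a valid analysis that gives up a little efficiency and is cheap to improve

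*SAP*

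**What the plan says.** SAP Section 5, Analysis methods, sets one adjustment rule for all secondary and tertiary outcomes: the effect is "estimated as difference in the outcome by randomisation group adjusted for the outcome at baseline". For yes/no outcomes the model is also fixed: "categorical outcomes will be analysed in generalized linear mixed models (family binomial, link logit) with a random effect for hospital". No other covariate is named.

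Four outcomes are yes/no versions of something finer:

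- IFG and IGT, in the tertiary list as counts and percentages (entries beginning "Impaired Fasting Glucose (n and" and "Impaired Glucose Tolerance (n and").
- Self-perceived health, secondary in hierarchy 2 (entry beginning "Self-perceived health, Excellent/Very good (n and").
- Perceived diabetes risk, tertiary, with moderate and high merged.

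Section 4, Baseline characteristics, lists the V1 measurements behind the first two in mmol/L: fasting glucose and 2-hour glucose. For self-perceived health it shows only the merged class ("Excellent/Very good (n and", as a percentage).

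Section 3, Confidence intervals and p-values, treats tertiary outcomes as descriptive. Secondary outcomes are tested by Holm-Bonferroni within a hierarchy that opens only if its primary outcome is significant.

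**The concern.** A yes/no baseline treats a woman just below the IFG cut-off at V1 like one far below it, although her chance of IFG at V2 is higher. In a randomised comparison, a logistic model with a stronger baseline predictor tests the arm effect with more power and no loss of validity. The plan already accepts baseline adjustment; for these outcomes it uses a coarser version of the baseline than the trial holds.

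What is at stake is precision, not bias. There is a smaller point of clarity too. The phrase could also be read as the underlying measurement, and the conditional odds ratio depends on which covariate is used. It is better to name the covariate in advance than to leave two readings open.

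**Working it through.** **The plan's own figures.** The SAP states no power for these four outcomes, only for BMI. With a difference of 1.0, SD 2.5, two-sided 5%, 80% power and 2:1 allocation, the usual-care group needs (1 + 1/2) × (1.960 + 0.842)² × 2.5² / 1.0² = 73.6, so 74, and 222 in total. With the t distribution 222 gives 79.9% and 225 gives 80.4%, so 225 is reproduced. Then 225/0.7 = 321.4, so 322, and 322/0.7 = 460. The checks below use 225 women, 150 against 75.

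**What a cut baseline keeps.** For a normal value cut so that a proportion p lies beyond c, the squared correlation between the value and its yes/no version is φ(c)² / [p(1 − p)]:

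- p = 10%: 0.1755²/0.09 = 0.34
- p = 20%: 0.2800²/0.16 = 0.49
- p = 30%: 0.3477²/0.21 = 0.58
- p = 50%: 0.3989²/0.25 = 0.64

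**Effect on power.** Inputs assumed because the SAP gives none: a latent normal value at V1 and V2, cut at the same point; usual-care prevalence 10% to 50%; correlation 0.3 to 0.8; latent arm shift 0.40 to 0.55 SD. Logistic regression of the V2 outcome on arm plus one baseline covariate, 4,000 runs per setting, rejection at |z| > 1.96, no hospital term. Power in %, for three of the correlations:

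| Prevalence | Correlation | Yes/no baseline | Continuous | Five-level score |
|---|---|---|---|---|
| 10% | 0.3 | 47.9 | 50.9 | 51.0 |
| 10% | 0.5 | 50.6 | 53.1 | 52.3 |
| 10% | 0.7 | 54.1 | 58.8 | 57.5 |
| 20% | 0.3 | 50.5 | 50.9 | 50.5 |
| 20% | 0.5 | 52.8 | 54.4 | 54.4 |
| 20% | 0.7 | 60.4 | 64.2 | 63.4 |
| 30% | 0.3 | 55.9 | 56.3 | 56.2 |
| 30% | 0.5 | 57.7 | 60.3 | 59.4 |
| 30% | 0.7 | 64.8 | 69.4 | 68.3 |
| 50% | 0.3 | 63.0 | 63.6 | 63.2 |
| 50% | 0.5 | 66.7 | 68.4 | 67.8 |
| 50% | 0.7 | 72.1 | 77.7 | 76.3 |

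At correlations 0.5 and 0.7 the gain is 1.6 to 5.6 points for the continuous value and 1.1 to 4.2 for the five-level score. At 0.3 it is 0.4 to 0.6 points for the continuous value, apart from 3.0 at prevalence 10%. That cell is sparse (75 × 10% = 7.5 expected events in usual care), and failed fits were counted as non-rejections, so it should not be read as pure efficiency. The simulation error of one cell is about √(0.5 × 0.5/4000) = 0.8 points; covariates were compared on the same simulated data.

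**Validity.** With no arm effect, at correlation 0.6 and prevalences 20% and 50%, rejection was 5.0% and 4.7% with the yes/no baseline, and 4.9% and 4.9% with the continuous one.

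**As relative efficiency.** Repeating the simulation with hospital terms gives, for a continuous baseline, about 1.01 to 1.02 at correlation 0.3, 1.04 to 1.05 at 0.5 and 1.10 to 1.12 at 0.7. For a five-level item it gives about 1.01 to 1.08. The power gain is about 1 to 5 points at 0.5 to 0.7. The table agrees: inverting power as [(z₂ + 1.96)/(z₁ + 1.96)]², with z the normal quantile of each power, gives 1.04 (prevalence 20%) and 1.06 (30%) at correlation 0.5, and 1.09 and 1.11 at 0.7. An efficiency of 1.04 to 1.12 is like 225 × 0.04 = 9 to 225 × 0.12 = 27 more women analysed.

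**The test actually planned.** Self-perceived health is one of four secondary outcomes in hierarchy 2, so the first Holm step is 0.05/4 = 0.0125, or |z| > 2.50. The power levels in the table are therefore not those of the planned test, but the gains at 0.0125 are similar.

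**The case against.** The strongest reply is that nothing is wrong. Adjusting an outcome for its own baseline value is prespecified, consistent and valid. IFG and IGT are descriptive, so no decision turns on their power. Fasting glucose (secondary) and 2-hour glucose (tertiary) are each analysed as continuous outcomes with their own continuous baseline. The one formally tested outcome affected, self-perceived health, sits behind the SF-12 mental component and Holm, and the SAP does not say that its separate answers are kept. The gain depends wholly on assumed inputs, including a single cut on one normal variable.

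Most of this stands, and it sets the weight of the point. A reader might infer that the plan wastes substantial power on the outcomes closest to diabetes risk. The documents do not support that: the glucose information is used in full in the continuous analyses, and the loss is close to nil at low correlation. A reader might also take the full answer to self-perceived health as documented. It is an inference from a label that joins two answers. For perceived risk, too, the inference comes from labels: the Secondary objectives refer to high risk alone, while the later lists merge moderate and high.

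The reply does not give a reason to keep the coarser covariate, which brings no statistical advantage.

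**Conclusion.** The point holds as a minor efficiency improvement, not an error. The likely loss is a relative efficiency of 1.04 to 1.12 for IFG and IGT if the baseline-to-V2 correlation is 0.5 to 0.7, almost nothing at 0.3, and up to about 1.08 for a five-level questionnaire item. These sizes rest on assumed prevalence, correlation, effect and a latent normal form. Type I error is unaffected. Formal inference is touched only for self-perceived health, and only if the SF-12 mental component is significant first.

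**What to change.** Add one sentence to Section 5, Analysis methods, before unblinding: yes/no outcomes derived from a measured or ordered variable are adjusted for the underlying V1 value. That means fasting glucose for IFG, 2-hour glucose for IGT, and the ordered V1 answer, entered as a linear score where it is held, for self-perceived health and perceived diabetes risk. Keep the logit link and the hospital term.

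No new data are needed. The small cost is that each odds ratio becomes conditional on a different covariate, so its size is not directly comparable with one adjusted for the yes/no baseline. Entering the value linearly is also a modelling choice, which the sentence should state.
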